5.2 Laboratory testing and sample shipping

The following laboratory tests are performed at each study visit during the first 12 months:

- Routine laboratory analyses, including complete blood count, basic metabolic panel, total protein, fasting glucose. These analyses will be performed by the Central Laboratory of Massachusetts General Hospital or at the patient's local Quest laboratory.
- Two 10 ml Streck Cell-Free DNA BCT® whole blood tubes are drawn and stored at 7°C pending shipment. Streck tubes are shipped at ambient temperature (between 6° and 37°C) to CareDx using the shipping material and instructions provided by CareDx.
- Two 2.5ml Paxgene® whole blood tubes are drawn and stored at -20°C pending shipment. These tubes are shipped on ice (-20°C) to Transplant Genomics.
- One 10 ml EDTA and one 10 ml SST tube will be collected, centrifuged at 4°C for 10 minutes at 3000 RPM. The resulting 5 ml of EDTA plasma and 5 ml of SST plasma will be stored at -80°C pending possible future analysis (i.e. biobanked).

Donor-specific antibody screening occurs at 1, 4, 7, 10, 12 and 24 months. These analyses will be performed by the HLA laboratory of Massachusetts General Hospital.

6. Statistics

Normality will be tested using the Shapiro-Wilk test. Average eGFR and proteinuria at baseline and 24 months will be compared using paired samples t test. A 2-sided p-value < 0.05 will be considered statistically significant. All analyses will be performed using IBM SPSS Statistics version 23 (IBM, New York, NY). Figures will be generated using Graphpad Prism version 6 (Graphpad Prism, La Jolla, CA).

7. Direct access to source data and document

The investigator and the institution will permit trial-related monitoring, audits, EC review, and regulatory inspections (where appropriate) by providing direct access to source data and other documents (e.g. subjects' case sheets, blood test reports, X-ray reports, histology reports etc).

8. Ethics and regulatory approvals

The trial will be conducted in compliance with the principles of the Declaration of Helsinki (2013), the principles of GCP and in accordance with all applicable regulatory requirements. This protocol and related documents will be submitted for review to the Ethics Committee.

The Study can and will be conducted only on the basis of prior informed consent by the Subjects, or their legal representatives, to participate in the Study. The Participating Site will obtain a signed informed consent form (ICF) for all subjects prior to their enrollment and participation in the Study in compliance with all applicable laws, regulations and the approval of the (local) Ethics Committee, if required. The Participating Site will retain such ICFs in accordance with the requirements of all applicable regulatory agencies and laws.

The Investigator and the Participating Site will treat all information and data relating to the Study disclosed to Investigator in this Study as confidential and will not disclose such information to any third parties or use such information for any purpose other than the performance of the Study. The

collection, processing and disclosure of personal data, such as patient health and medical information is subject to compliance with applicable personal data protection and the processing of personal data.

9. Data Handling and Management

The principal investigator is responsible for monitoring efficacy and safety every time a patient presents to the transplant clinic, which in principle is monthly for the duration of the study. An adverse event tracking log will be kept and unanticipated adverse events will be reported to Partners' IRB within 5 working days, in accordance with PHRC guidelines for adverse event reporting.

The PI is responsible for monitoring the validity and integrity of the data and adherence to the IRB-approved protocol.

Most of the information collected on subjects throughout this study is stored in the Electronic Medical Record (Epic) as part of routine clinical care. This includes vital parameters, laboratory results (including Allosure results, which are reported in Epic), reported adverse events and clinical findings on monthly outpatient visits. Relevant findings are extracted to an anonymized spreadsheet. Only the (co-)principal investigators will have access to the file that links patient names to anonymized identifiers. Paper informed consent documents are stored securely in the Department of Nephrology.

10. Financial Aspects

The study is financed by the companies CareDx and Transplant Genomics.

11. References

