Study protocol

Immune monitoring to facilitate belatacept monotherapy

1. Synopsis

Title	Immune monitoring to facilitate belatacept monotherapy
Study design	Prospective single-center, single-arm pilot study
Study center	Massachusetts General Hospital
Principal investigator	[name]
Co-investigators	[name]
Objectives	
1. To determine the percent of belatacept-treated renal transplant patients that can be safely converted to belatacept monotherapy2. To determine the utility of novel immune monitoring tools to facilitate belatacept monotherapy
Primary endpoint	Occurrence of biopsy-proven acute rejection
Secondary endpoints	
- Change in eGFR (CKD-EPI)- Appearance of proteinuria- Appearance of de novo donor-specific antibodies- Overall and death-censored graft survival
Sample size	20
Summary of inclusion criteria	
- Age 18 years or older- Written informed consent- Single kidney transplant recipient (i.e. no combined organ transplants)- Treated with belatacept- At least 1 year after transplantation or after initiation of belatacept- Stable renal function- Blood biomarkers indicate immune quiescence- No history of biopsy-proven acute rejection- Absence of donor-specific antibodies (at any MFI)- No history of BK viremia in current allograft

	
 - Spot urine protein/creatinine ratio < 0.5 g/g
Maximum duration of follow-up per participant	24 months after inclusion
Protocol version	Version 1.4 (10/25/2019)
Version and date of protocol amendments	N/A

2. Background

Belatacept is a selective costimulation blocker that is a non-nephrotoxic alternative to the calcineurin inhibitors cyclosporine and tacrolimus. In renal transplantation, belatacept has demonstrated similar graft and patient survival compared with cyclosporine, but is associated with superior renal function and lower rates of donor specific antibody (DSA) development.^{1,2}

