3.2 Trial design

Prospective single-center, single-arm interventional pilot study

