3.3 Primary endpoint at 24 months

- Occurrence of biopsy-proven acute rejection

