3.4 Secondary endpoints at 24 months

- Change in eGFR (CKD-EPI)
- Appearance of proteinuria
- Appearance of de novo donor-specific antibodies
- Overall and death-censored graft survival

4. Selection and withdrawal of subjects

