5.1 By visit

For all belatacept-treated patients, monthly visits in the outpatient clinic, where belatacept infusions are administered, are part of routine clinical care. Trial visits will coincide with these infusion visits, occurring monthly for the first year after inclusion. At study visits, subjects are questioned and examined by a physician and blood samples are drawn (see below). For patients who receive monthly belatacept infusions at home, they will have blood samples (clinical and research specimens) drawn at their local Quest laboratory and the study physician will call them to assess for adverse events. If any adverse events are noted, a telemedicine or in-person visit with a transplant nephrologist will be scheduled at the discretion of the investigator.

Reduction of immunosuppression occurs in a stepwise fashion, whereby each reduction is contingent on several factors:

- Renal function is stable, defined as eGFR no more than 20% lower compared to value at inclusion
- Both the Allosure and Trugraf tests indicate a state of immune quiescence. For the Allosure, this corresponds to a dd-cfDNA concentration of < 1%; for the Trugraf test, this corresponds to a "TX" signature.
- No appearance of any de novo DSA (at any MFI) at any previous point during study
- No proteinuria > 0.5 g/g creatinine on spot urine sample

If, at any point, a patient does not fulfill all of the abovementioned criteria, immunosuppression will not be (further) reduced. In such cases, the principal investigator will decide whether to continue with the reduced-intensity immunosuppressive regimen or revert back to conventional triple therapy (belatacept + mycophenolate/mTORi + steroids).

Criteria for performing a kidney biopsy are:

- Unexplained decrease in eGFR > 40% from baseline value
- Occurrence of new proteinuria > 1.0 g/g creatinine on 2 separate random urine samples

The principal investigator can decide to perform a kidney biopsy in patients who do not strictly meet the abovementioned criteria, if the probability of rejection is felt to be high, i.e. a combination of abnormalities such as new DSA and proteinuria < 1 g/g, or a very high (>3%) Allosure result combined with a mild (20%) decrease in eGFR.

In case of a discrepancy between Allosure and Trugraf results (i.e. Allosure < 1% but Trugraf positive for rejection), immunosuppression will not be weaned further.

Study timeline

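### The 24-month eGFR endpoint is analysed only by a test of difference at n = 20, so a non-significant result would not show that renal function was preserved

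*Combined protocol and SAP*

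**What the plan says.** The synopsis and Section 3.1 set out to find what percentage of patients can safely move to belatacept monotherapy. Section 3.2 describes the design as "Prospective single-center, single-arm interventional pilot study", and the synopsis gives "Sample size 20" without a justification. The primary endpoint in Section 3.3 is "Occurrence of biopsy-proven acute rejection". Change in eGFR is one of four secondary endpoints at 24 months in Section 3.4.

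The planned analysis of eGFR is one sentence in Section 6: "Average eGFR and proteinuria at baseline and 24 months will be compared using paired samples t test". The criterion follows: "A 2-sided p-value < 0.05 will be considered statistically significant". The section gives no confidence interval, margin, clinically relevant mean loss, SD or power.

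Elsewhere the protocol does say what it means by stable function in an individual. Section 5.1 makes each reduction conditional on this: "Renal function is stable, defined as eGFR no more than 20% lower compared to value at inclusion". Section 4.4 uses a confirmed fall of more than 20% to halt further weaning, and Section 5.1 lists an unexplained fall of more than 40% as a biopsy criterion. Section 6 uses none of these limits for the month-24 results.

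**The concern.** The question for eGFR is whether function held up after weaning. The planned test has no change as its null hypothesis and can only produce evidence against it. A small sample or noisy measurements make a non-significant result more likely whatever happened to the kidneys. There is no control arm and no planned interval, so a reader given only the p-value cannot tell preserved function from imprecision.

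A test of the mean has a second weakness here. If a few participants lose a lot of function and the rest are stable, those losses move the mean only a little and inflate the SD in the denominator of the test. The protocol's 20% limit would identify such participants, but it is not carried into the analysis. What is at stake is the renal part of the conclusion on safe conversion.

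**Working it through.** **Inputs from the protocol.** n = 20 (synopsis); paired t test, two-sided 0.05 (Section 6); eGFR above 40 ml/min for entry (Section 4.1); 20% limit for stable function (Section 5.1).

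**Inputs assumed.** SD of the 24-month change: 6 to 15 ml/min. True mean losses: 4, 5 and 8 ml/min. The protocol states neither an SD nor a relevant mean loss. The 8 ml/min is 20% of the eGFR floor (0.20 × 40); it borrows a patient-level limit for scale and is not a margin for the mean.

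**The plan's own figure.** The sample size of 20 cannot be reproduced, because no effect size, SD, power or precision target is given.

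**Step 1: precision.** Half-width of the 95% CI = t(0.975, 19) × SD / √20 = 2.093 × SD / 4.472 = 0.468 × SD. If the observed mean change is exactly zero, the half-width is also the largest mean loss that the interval does not exclude.

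**Step 2: chance of a non-significant result.** Non-central t distribution, 19 degrees of freedom, non-centrality = (mean loss / SD) × √20. Example: loss 5, SD 10 gives 0.5 × 4.472 = 2.24, and a non-significant result in 44% of trials.

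| SD of change (assumed) | 95% CI half-width | Loss of 4 missed | Loss of 5 missed | Loss of 8 missed |
|---|---|---|---|---|
| 6 | 2.8 | 19% | 6% | <1% |
| 8 | 3.7 | 44% | 24% | 1% |
| 10 | 4.7 | 60% | 44% | 8% |
| 12 | 5.6 | 71% | 58% | 19% |
| 15 | 7.0 | 79% | 71% | 38% |

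Losses and half-widths are in ml/min.

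**Step 3: detectable loss.** Power of 80% needs a mean loss of 0.66 × SD: 4.0, 5.3, 6.6, 7.9 and 9.9 ml/min for the five SDs.

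**Step 4: missing values.** With 16 complete pairs instead of 20, the half-width rises to 0.533 × SD, which is 4.3 ml/min at SD 8 and 8.0 ml/min at SD 15.

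**Step 5: a few large losses (illustration, assumed values).** Let 3 of 20 participants lose an extra 20 ml/min while the other 17 have no mean change, with SD 6 around these values.
- Mean loss = 3 × 20 / 20 = 3 ml/min.
- The shift adds 400 × (3 × 17 / 20) / 19 = 53.7 to the variance of 36, so the SD rises from 6 to about √89.7 = 9.5.
- By simulation the paired t test is non-significant in about 83% of trials.
- If exactly those three fall below the 20% limit, the count is 3/20 = 15%, exact 95% CI 3% to 38%.

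A count of 0/20 has an exact upper 95% limit of 1 − 0.025^(1/20) = 17%.

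**Step 6: is two-sidedness the cause?** No. A one-sided 0.05 test would still miss a loss of 5 ml/min in 3%, 15%, 31%, 44% and 58% of trials at SD 6, 8, 10, 12 and 15. The causes are the small sample and the absence of an interval.

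**The case against.** A reader might infer that the trial judges renal safety by this test, or that a clinically relevant loss would often be passed off as no change. The documents support neither.

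- **Role of the test.** eGFR is a secondary endpoint beside proteinuria, de novo donor-specific antibodies and graft survival, and the primary endpoint is rejection. Individual patients are protected by the 20% and 40% rules. This stands. Those rules govern weaning and biopsy during follow-up, however, and do not summarise renal function at month 24.
- **Interpretation.** Nowhere does the protocol say that p > 0.05 will be read as preserved function, and no decision rule links the eGFR p-value to the conversion objective. This also stands. The gap is that nothing planned would let a reader draw the correct conclusion.
- **Frequency.** Whether a loss is often missed depends on an SD and a relevant loss that the protocol does not state. A 5 ml/min loss at SD 6 is missed in only 6% of trials, and an 8 ml/min mean loss in 1% to 19% at SD 8 to 12. This stands, so no general claim about frequency is made here.
- **Pilot status.** Limited power on a secondary endpoint is inherent in a 20-patient pilot, and no change of analysis removes it. True, but this argues for reporting estimates with their precision rather than a significance verdict.
- **Optional extra.** The 20% limit is a weaning rule, not a named month-24 endpoint, so counting patients beyond it adds an analysis rather than correcting an error. That is fair. It is still the protocol's own definition of stable function, and it shows what the mean can hide.

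**Conclusion.** The concern holds in a limited form. The only planned analysis of the 24-month eGFR endpoint is a test of difference, and at n = 20 a non-significant result from it is not evidence of preserved function. With an assumed SD of change of 8 to 15 ml/min, even an observed mean change of zero leaves a mean loss of about 4 to 7 ml/min unexcluded, and a few large individual losses can leave the test non-significant.

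The absence of an interval and of a month-24 use of the 20% limit can be read directly from Section 6. The sizes rest on assumed SDs and on 20 complete pairs; fewer pairs would widen the intervals. It is a worthwhile correction to a secondary analysis, not a flaw in the primary endpoint.

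**What to change.** In Section 6:

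1. Make the mean change in eGFR from inclusion to month 24, with its 95% CI, the main eGFR result. The paired t test p-value may stay as supportive.
2. Add the number and percentage of participants whose month-24 eGFR is more than 20% below inclusion, with an exact 95% CI, and state the denominator.

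The cost is two sentences and no new data, since eGFR at inclusion and at month 24 is already needed for the planned test. The downside is that the renal conclusion will look less favourable when the intervals are wide; even no participant out of 20 beyond the limit would carry an upper bound of 17%. No clinical rule changes.
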